We predict that a musical listening exercise will more effectively contribute to the facilitation of sleep compared to non-musical sounds and compared to standard of care on the GAU. We plan to conduct this study as a feasibility study. It will be a 3-arm randomized controlled trial where participants will be randomized to either: (1) music listening intervention, (2) non-musical sounds involving nature sounds, or (3) standard of care on the GAU. The intervention will take place over 7 consecutive nights.

The primary outcome will be sleep quality, which will be measured objectively using sleep logs and subjectively through patients' own perspectives of their sleep through the Insomnia Severity Index. Secondary outcomes will include patients' sleep quality assessed by smart watches, which we will evaluate to see if the data correlates to the sleep logs and patients' subjective view of their sleep. Other secondary outcomes will include patients' mood, level of pain, number medications used for sleep, duration of stay in hospital, patients' level of enjoyment of the music or non-musical sounds, and feasibility measures.

As this is a feasibility study, the goal is to show that it is possible to conduct a larger study with the same objectives and methodology. The ultimate goal is to create high-quality evidence to support (or refute) our hypothesis that music listening interventions are effective at facilitating sleep for patients admitted to the GAU. This would be a safe and cost-effective intervention to improve the health outcomes of this vulnerable population.

Background/literature review:

Impact of sleep disturbance in older adults

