sleep) [35]. Masking was identified as having support for improving sleep, relaxation, distraction, and enjoyment had mixed levels of support, expectation had possible support, and entertainment had mixed possible support [35].

The use of music listening interventions for the improvement of sleep quality specifically in older patients has been shown to be effective in two recent systematic reviews and meta-analyses [15, 36]. The systematic review by Chen 2021 included 5 studies of older patients in the community for whom the music interventions took place over weeks. It found that music is a safe and effective non-pharmacological intervention for improving the sleep quality of community-dwelling elderly people [15]. The systematic review by Wang in 2021 included 9 studies, 6 of which were included in the meta-analysis. The results of the post-hoc meta-analysis indicated that music interventions might have a positive effect on sleep quality, but that more randomized controlled trials are required [36].

To the best of our knowledge, there has not been a randomized controlled trial evaluating the effect of music listening on sleep quality in geriatric patients hospitalized in the acute care setting, nor have there been trials with carefully selected/controlled music stimuli. Therefore, there is still a need for more high-quality evidence to support how music interventions can effectively be used for the facilitation of sleep for geriatric patients hospitalized in the acute care setting, over a shorter period of time, and how this intervention could potentially improve other health outcomes in this vulnerable population.

Purpose:

The purpose of this study is to examine the impact of music listening interventions on the facilitation of sleep and the improvement of sleep quality for patients admitted to the geriatric assessment unit (GAU), as well as the feasibility of applying these interventions.

Hypothesis:

We predict that a musical listening exercise involving instrumental slow-tempo music (STM) will more effectively contribute to the facilitation of sleep compared to non-musical sounds (nature sounds) and compared to standard of care on the GAU which involves an adapted in-hospital approach to geriatric patients.

Study methods:

Study design:

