We plan to conduct this study as a feasibility study. It will be a 3-arm randomized controlled trial where participants will be randomized to one of the three following groups: music listening intervention involving instrumental STM, non-musical sounds involving nature sounds, or standard of care on the GAU (control). The patients will be randomized in equal ratios to the 3 groups using a random number generator. Each intervention will take place over 7 consecutive nights. The music or non-musical sounds will be played throughout the whole night for each patient in those groups.

We note that patients' medical situation will likely change throughout their hospitalization stay and this may be a confounding factor affecting their sleep. We also note that patients may be discharged prior to completing the 7-day intervention.

Selection of music and non-musical sounds:

The music selected in our study will be pleasant instrumental STM in a major mode. It will also be low contrast (without periods of silence). The non-musical sounds will be low-contrast nature sounds such as waves. We plan to use non-musical sounds that align with the frequency range of the musical stimuli.

Study outcomes:

The primary outcome to be measured will be sleep quality. This will be measured objectively by sleep logs and subjectively through patients' own perspectives of their sleep.

Secondary outcomes will include patients' sleep quality assessed by smart watches. We will evaluate if the data from the smart watches correlates to patients' sleep log and to their subjective view of their sleep quality.

Other secondary outcomes will include the patients' mood (depression, anxiety), level of pain, the number medications used for sleep (PRNs and regular medications), and the duration of stay in hospital. Of note, as part of our study, we will not be administering any medications to the patients, and we do not expect there to be any alcohol use on the GAU. We will simply be taking note if the patients received any medications for the indication of facilitating their sleep, prescribed by their treating physician. On the GAU, the patients will be assessed daily their treating physician for their medical management.

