Sleep logs will be used to clinically track patients' sleep (bedtime, sleep onset, wake time) (appendix 3). This information will be gathered by the research assistants from the nursing report in the morning after the night shift. The number and duration of naps that patients take during the day will also be tracked. Subjective measures of sleep will be assessed via the Insomnia Severity Index (ISI) questionnaire (appendix 4) which will be administered to the patients daily. The ISI questions will be slightly modified so that the questions focus on patients' latest night of sleep, not on their sleep over the past 2 weeks, as this questionnaire will be administered daily. The ISI has been shown to be a reliable and valid tool as an outcome measure in insomnia treatment and research in older patients [38]. The ISI has been used in previous studies for older patients [39-41].

The patients will wear smart watches (Samsung Galaxy Fit2) at all times throughout the study period. The smart watches assess sleep quality by tracking a set of non-staging sleep parameters including total sleep time, sleep onset latency, wake after sleep onset, and sleep efficiency. Smart watches have shown good inter-test reliability (96-99%) when assessing sleep parameters in individual adults, and although more limited in comparison to laboratory-based polysomnography, smart watches can allow for the examination of changes within individual patients [42]. The data collected from the smart watches will be time stamped and extracted by the study investigator without any identifying information. We will assess if the data from the smart watches correlates to patients' sleep logs and their subjective view of their sleep quality.

The data on patients' mood will be assessed via visual analog mood scales of specifically 8 emotions: afraid, confused, sad, angry, energetic, tired, happy, and tense (appendix 5). These will be administered to the patients daily throughout the study period. Pain will also be assessed via a visual analog scale that the patients will be asked to answer daily (appendix 6). The data on the number of medications used for sleep (PRNs and regular medications) will be gathered at the nursing report in the morning after the night shift. The data on duration of stay in hospital will be gathered via chart review.

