Furthermore, we will gather data on how much the patients enjoy the selected music and non-musical sounds in our study by asking them to rate their music enjoyment on a scale of 0 to 10 and by noting their qualitative comments on the music or non-musical sounds. These questions will be asked to the patients daily.

Data on protocol adherence, specifically whether the patients kept their headphones on throughout the night, or whether they turned the music off (by checking the mp3 player), will be gathered at the nursing report in the morning after the night shift. Furthermore, we plan to measure the noise present around the patients at night by placing a sound recorder at their bedside.

Lastly, we will note whether patients are in the bed next to the window in their hospital room (most rooms have double occupancy – bed A or B), to examine if light exposure may have had an impact on their sleep. We also recognize that light exposure will change over the 6-month study period as the seasons change and may impact patients' overall sleep quality.

The data collection will take place over the 6-month study period (March to August 2022) and will be put together for analysis over the following months. The data analysis will take place over the 4 months following the study period and will be completed by December 2022.

Sample size:

As this is a feasibility study, we aim to enroll around 50 participants in the study, estimating that 2 patients will be enrolled every week. This sample size estimation is based on previous similar studies. A randomized controlled trial conducted in 2017 in the same patient population, specifically patients admitted to the GAU at St. Mary's Hospital, included 36 patients [22]. This study examined the effect of music on patients' health, specifically their emotions and mobility [22]. Furthermore, most of the studies included in two recent systematic reviews and meta-analyses examining the impact of music for the improvement of sleep quality in older patients in the community had sample sizes mostly between 40 and 60 patients [15, 36].

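### The primary sleep log is called objective but comes from nurses who can see who has audio, and correlating it with the watch cannot reveal over-recording in the audio arms

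*Protocol*

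**What the plan says.** **Label.** The Abstract says of the primary outcome, sleep quality: "which will be measured objectively using sleep logs and subjectively through" the patients' own view. Study outcomes repeats it: "This will be measured objectively by sleep logs and subjectively through" the patients' own view.

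**Source.** Data collection procedure defines the log as bedtime, sleep onset and wake time and adds: "This information will be gathered by the research assistants from the nursing report in the morning after the night shift".

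**Knowledge of allocation.** The same section takes adherence from that report, both headphone wear and "whether they turned the music off (by checking the mp3 player), will be gathered at the nursing report". Study design has audio playing all night in two of the three arms. No masking or sham is described.

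**Log against watch.** The watch is a secondary outcome, worn in all arms. The Abstract describes its data as something "which we will evaluate to see if the data correlates to the sleep logs". Data collection procedure says "We will assess if the data from the smart watches correlates to" the logs and the patients' own view. Data analysis lists group tests, regression and repeated-measures ANOVA, and no agreement analysis.

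**Control arm.** The schematic flow lists headphone and mp3-player adherence for the control group too, although that group receives standard of care.

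**The concern.** The log is a human judgement of when someone fell asleep and woke, made by staff who can be taken to know whether the patient is wearing an audio headband. A patient lying still with a headband on may be logged as asleep sooner or for longer than a similar patient without one. If so, music gains a spurious benefit in one of the two comparisons in the Hypothesis, which tests music "compared to non-musical sounds (nature sounds) and compared to standard of care on the GAU". It would gain it on the measure presented as objective. The other primary component, the ISI, is patient-reported with no masking described, so it gives no independent protection.

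A watch on every wrist could help to reveal this, but not through correlation, which ignores differences in level. The protocol wants a larger study with the same objectives and methodology, so whether the log is fit to serve there is worth learning now.

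Two limits apply. Nurses need not know music from nature sounds, so this mechanism does not favour either audio arm over the other. A constant shift within an arm also leaves that arm's SD unchanged, so the SD the study wants for future planning is not damaged by it.

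**Working it through.** **The plan's own figures.** Sample size gives about 50 participants at 2 per week over six months: 2 × 26 = 52, which agrees. Equal allocation to three arms gives about 17 per arm (51 in all). No SD, effect size or error rate is stated.

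**What needs no assumption.** Write watch = T + e₁ and log = T + e₂ + d in the audio arms (d = 0 in control). Within an arm d is constant, so the log–watch correlation there does not depend on d.

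**Assumed inputs, none from the protocol (minutes).** True onset-to-wake SD T = 90; nurse error L = 60; watch error W = 45; over-recording d = 30, range 20 to 45; no true effect. Two thirds of patients have audio, so the shift adds d² × (2/3)(1/3) = 2d²/9 to the pooled log variance.

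**A. One value per patient.**

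Pooled r = T² / √[(T² + L² + 2d²/9)(T² + W²)]

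- d = 0: 8100 / √(11700 × 10125) = 0.744
- d = 30: 8100 / √(11900 × 10125) = 0.738
- d = 20: 0.741; d = 45: 0.730

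The 95% interval for r = 0.744 at N = 51 is 0.59 to 0.85, so none of these shifts could be noticed.

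Log SD within an arm = √(90² + 60²) = 108. Chance of a significant music–control difference with no true effect (two-sided 5% t-test, 17 v 17, noncentral t):

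| d (min) | 5 | 10 | 20 | 30 | 45 |
|---|---|---|---|---|---|
| one value per patient | 5.2% | 5.8% | 8% | 12% | 22% |
| 7-night means (B) | 5.4% | 6.5% | 11% | 19% | 37% |

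With T from 60 to 120 and L from 30 to 90, d = 30 gives 9% to 24% with one value per patient, and r falls by no more than 0.016.

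**B. Seven-night means.** Each variance is multiplied by ICC + (1 − ICC)/7. With true ICC 0.5 the factor is 0.571; with error ICC 0.3 it is 0.400. Log SD = √(8100 × 0.571 + 3600 × 0.400) = 77.9. Pooled r goes from 0.806 to 0.793 at d = 30.

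**What the paired difference would show.** In log minus watch, T cancels. Its SD is √(60² + 45²) = 75 for one value, and 75 × √0.400 = 47.4 for 7-night means. For one audio arm v control, half-width = 2.037 × SD × √(2/17):

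| error ICC (7-night means) | SD | half-width | power for 30 min | power for 15 min |
|---|---|---|---|---|
| 0 | 28 | 20 | 85% | 32% |
| 0.3 | 47 | 33 | 43% | 15% |
| 1 (same as one value) | 75 | 52 | 20% | 9% |

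The 15-minute column is the case where the watch shares half of a 30-minute bias. The overall mean difference (n = 51) has half-width 8, 13 and 21 min in the three rows.

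For contrast, the arm comparison on the watch alone (error ICC 0.3) has half-width about 51 min at true ICC 0.5, and 45 to 66 min for true ICC 0.3 to 1.

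**Separate check with different inputs.** True SD 1.0 to 1.5 h, error SD 0.5 to 1.0 h, both audio arms (33) v control (17), d = 0.5 h. Within-arm r is unchanged. Pooled r moves from 0.692 to 0.686 in one case and 0.800 to 0.783 in another. The false-positive rate is 15% to 32%.

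**The case against.** - **The detail belongs in a SAP.** Agreement methods are often left there, and the protocol names no coefficient. That is fair for the mechanics. But the label, the data source and the wish to see whether log and watch correlate are all stated in the protocol, and the first and last are what need changing.
- **Correlation was never offered as a bias check.** True. It is nonetheless the only log–watch comparison stated, so as written nothing planned tells the next study whether the two agree in level.
- **The watch is compared by arm anyway.** It is a sleep outcome in all arms, so its arm effect can be set beside the log's. This stands as a partial check, but a less precise one: about 51 against 33 min half-width.
- **The bias is hypothetical.** This stands. Nothing in the protocol shows over-recording, and at 5 to 10 minutes the error rate stays close to 5%.
- **The remedy is weak.** This also stands. It has about 43% power for 30 minutes, and less if the watch too reads stillness as sleep. The protocol itself calls such watches "although more limited in comparison to laboratory-based polysomnography".
- **Objective only means not self-reported, and this is a feasibility study.** The contrast may be what was meant, but readers will take the word to mean free of observer judgement. Group comparisons are planned, and the larger study would inherit the measure.

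**Conclusion.** The concern holds. The primary log is an observer's record from a source that also reports who has headphones on, and calling it objective misdescribes it. Correlation cannot detect over-recording confined to the audio arms: exactly so within arms, and nearly so pooled, where a 30-minute bias shifts r by 0.006 (one value per patient) or 0.013 (7-night means).

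The false-positive figures of 12% and 19% at 30 minutes rest wholly on assumed SDs, ICCs and bias; over 20 to 45 minutes the range is 8% to 37%. They concern audio against standard care only. This is a should-fix point held with medium confidence: the risk is plausible but not shown to occur, and the correction is cheap.

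**What to change.** 1. In the Abstract and Study outcomes, describe the log as nurse-observed and not masked to audio versus standard care, in place of objective.
2. For log against watch, report the mean difference with limits of agreement, allowing for repeated nights, overall and by arm, as estimates with intervals. This can replace correlation or stand beside it. Keep correlation for watch against ISI, where the scales differ.
3. Match the quantities first. Compare sleep onset with sleep onset, since watch data are time stamped. If the log records no night waking, compare its onset-to-wake interval with watch total sleep time plus wake after sleep onset. The log form (Appendix 3) is not shown, so this must be checked against it.
4. Reconcile the headphone and player item in the control group's schematic with standard of care.

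The cost is a few wording changes and a modest extra analysis of data already collected in every arm. By-arm estimates will be imprecise (half-width about 33 min under the assumptions above), and the watch may share part of the bias. A null difference therefore would not clear the log, and a clear difference would not by itself prove the log wrong. The report should say so.

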We will also assess how much the participants enjoy listening to the selected music and non-musical sounds in our study throughout the intervention. We will not include the MMSE as part of our outcomes as it is often unreliable when patients are admitted to hospital with an acute illness and may not be at their cognitive baseline.

Other secondary outcomes will include feasibility measures: the number of participations and refusals, the number of eligible patients and exclusions, protocol adherence, the availability of the data, the time

needed to collect the data, the cost, and the standard deviation of the primary outcome measures to help estimate the sample size required to achieve sufficient statistical power in subsequent studies.

Study population:

This study will include patients admitted to the GAU at St. Mary's hospital in Montréal over the six-month study period (March to August 2022). As many of the patients admitted to the GAU have major neurocognitive disorder (MNCD), we will include them in our study (MNCD of any stage, including Alzheimer's disease). Furthermore, we will include patients who take medications for sleep in our study, and they will be randomized into the 3 groups like all the other participants. We will only include patients who accept to participate in the study with consent obtained either for the patient or from their substitute decision maker if they are deemed not capable of providing consent (to participate in this research project) themselves by their treating physician.

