The patients' baseline characteristics will be noted upon entry into the study: admitting diagnosis, demographics (age, sex) and music sophistication. Patients' music sophistication will be evaluated using the General Musical Sophistication Subscale (GMSS) which is embedded within the Goldsmiths Musical Sophistication Index (Gold-MSI) and includes 18 items with excellent internal consistency (appendix 1) [37]. Furthermore, patients' normal sleep hygiene/routine will also be evaluated prior to the intervention specifically to see if they already listen to music or non-musical sounds before/while they sleep. Finally, as we will be including patients who use medications for sleep in our study, we will note what type of medication(s) the participants are taking. Specifically, we will categorize the medications in the following categories: benzodiazepines, antidepressants, antipsychotics, melatonin, or other; and we will note if the indication is specifically for sleep or not.

The following patients will be excluded from our study: patients who already listen to music or nonmusical sounds as part of their sleep routine, those with medical instability which limits their ability to participate in the study (determined by the patient's treating physician), those who have a diagnosis of a sleep disorder including obstructive sleep apnea and REM sleep behaviour disorder, and those who are unable to communicate in English or French. Furthermore, we will exclude patients with behavioural issues that limit their participation in the study; specifically, those that have agitation or hyperactivity that limits their compliance with the intervention as can be seen in cases of severe BPSD or hyperactive delirium. We will discuss with the treating physician to determine if the patient's behavioural issues would limit their ability to participate in the study and thus require exclusion from the study. Finally, we will also exclude patients with severe hearing impairment, specifically those for whom their hearing impairment affects their ability to communicate their consent for this study and to listen to music.

Recruitment and consent:

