A power calculation cannot be done as this is a feasibility study and there is too much patient heterogeneity with respect to medical and cognitive status to apply a power analysis from more homogenous study populations to the current study. We plan to use the results of this study to help determine the sample size required to achieve sufficient statistical power in a subsequent larger study with the same objectives and methodology.

Data analysis:

The participants' baseline characteristics will be summarized using means and standard deviations or frequencies and percentages, as appropriate. Between-group comparisons will be performed using unpaired sample t-test, Mann-Whitney, and/or Chi-square test, as appropriate. Multiple linear or logistic regression models will be used to identify whether the interventions influenced sleep outcomes. We will likely also utilize repeated-measure analysis of variance, to assess outcomes in our study.

Infection control:

Given the context of the ongoing COVID-19 pandemic, we will ensure infection control measures throughout our study. All equipment used in this study will be sanitized with Clorox between patients

Music Interventions for the Facilitation of Sleep in the Acute Geriatric Setting

(smart watches, headphones, mp3 players, and sound recorders). Standard infection control protocol on

the GAU at St-Mary's Hospital will be followed by the study investigators and research assistants.

Feasibility of this study:

[name], Geriatric Medicine Fellow at McGill University will be responsible for coordinating

this project. She will oversee the recruitment process of the participants (detailed above) and the data

collection for this study. Furthermore, 3 research assistants will be recruited to aid in enrolling patients

and for data collection. The study will also require the necessary equipment including the smart watches,

headphones, and music players. The study will be funded by the St. Mary's Hospital Foundation who will

provide 15 000\$.

Budget:

-Research assistants: Estimated work of 4 hours per day, 7 days per week. Salary 18\$/hour.

Total cost 13 000\$ for 6 months. The work will be divided between 3 research assistants.

-Equipment: Smart watches: 4 smart watches = 4 x 70\$ = 280\$ (+tax & shipping)

Headphones (sleep headbands) = 4 x 30\$ = 120\$ (+tax & shipping)

Bluetooth MP3 players = 4×40 \$ = 160\$ (+tax & shipping)

Sound recorder = 4×40 \$ = 160\$ (+tax & shipping)

-Total budget: 13 270\$.

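### Minor: repeated-measures ANOVA, named tentatively, classically drops patients without all 7 nights although early discharge is foreseen; using all observed nights is a cheap improvement

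*Protocol*

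**What the plan says.** The Study design section sets 7 consecutive nights per patient and adds: "We also note that patients may be discharged prior to completing the 7-day intervention". It gives no expected rate. The same section warns that "patients' medical situation will likely change throughout their hospitalization stay and this may be a confounding factor affecting their sleep".

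Under Data collection procedure, the sleep log is compiled each morning from the nursing report, and the ISI is a "questionnaire (appendix 4) which will be administered to the patients daily". Together these are the primary outcome, so each patient contributes up to 7 correlated values.

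The Data analysis section names t-test, Mann-Whitney and chi-square for comparing groups. It then says: "Multiple linear or logistic regression models will be used to identify whether the interventions influenced sleep outcomes". After that comes the sentence at issue: "We will likely also utilize repeated-measure analysis of variance, to assess outcomes in our study". No mixed model or similar method is mentioned, and the section does not say what happens to a patient with fewer than 7 nights.

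The feasibility measures under Study outcomes include "the standard deviation of the primary outcome measures to help estimate the sample size required to achieve sufficient statistical power in subsequent studies".

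**The concern.** Two statements in the protocol fit together poorly. One expects incomplete series. The other names, as the only method built for repeated measures, one whose classical form needs a full set of nights from every patient. Under that form a patient discharged after night 5 contributes nothing, although five nights were collected.

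The certain cost is precision, whatever the reason for leaving. With about 17 patients per arm, losing a few is noticeable. Two further effects are conditional. If patients who sleep better leave sooner, the remaining completers give a distorted arm contrast. If the planning SD is then computed from completers, it comes out somewhat small for sizing the next trial.

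**Working it through.** **Planned size.** Two patients per week over about 26 weeks (March to August) gives 2 x 26 = 52, which agrees with the stated target of around 50. Three equal arms give about 17 each. There is no power calculation to reproduce.

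**Assumptions, none from the protocol.** Constant daily discharge probability h; every patient has night 1, so there are 6 chances to leave before night 7; between-patient SD 4 and night-to-night SD 4 ISI points; discharge unrelated to sleep unless stated.

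**Patients and nights lost.**
- Share with all 7 nights = (1-h)^6. At h = 5%: 0.95^6 = 73.5%, so 50 x 0.265 = 13.2 patients are dropped.
- Nights observed = 50 x sum of (1-h)^k for k = 0 to 6. Nights discarded = 50 x [that sum - 7(1-h)^6]. At 5%: 302 observed, 44 discarded (15%).

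**Standard error of a two-arm contrast, variances known.**
- Completers: square root of (16 + 16/7) x (1/n1 + 1/n0), with n1 and n0 the completers per arm. At 5%, 17 x 0.735 = 12.5 per arm gives sqrt(18.29 x 2/12.5) = 1.71. Averaging over the random number of completers gives 1.73.
- Mixed model: each patient weighted by 1/(16 + 16/T), with T nights observed.
- Patient mean of observed nights: equal weights.

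| Daily discharge (assumed) | All 7 nights | Dropped of 50 | Nights discarded | SE completers | SE mixed | Excess |
|---|---|---|---|---|---|---|
| 1% | 94.1% | 2.9 | 10 | 1.51 | 1.47 | 3% |
| 2% | 88.6% | 5.7 | 20 | 1.56 | 1.48 | 6% |
| 3% | 83.3% | 8.4 | 28 | 1.62 | 1.49 | 9% |
| 5% | 73.5% | 13.2 | 44 | 1.73 | 1.50 | 15% |
| 8% | 60.6% | 19.7 | 64 | 1.92 | 1.52 | 26% |

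With patient-to-night SD ratios from 0.5 to 2, the excess at 3%, 5% and 8% is roughly 7-10%, 13-17% and 22-30%. The patient mean costs only about 1% against the mixed model at the base SDs, and up to 6% at ratio 0.5.

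**Bias, if discharge is related to sleep.** Simulation at 5% daily discharge, assumed true difference -4 points, 3000 runs per scenario (simulation error about 0.03):

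| Log-odds of discharge per SD of better sleep | Completers | Patient mean | Mixed model |
|---|---|---|---|
| 0 | -4.01 | -4.02 | -4.02 |
| 0.5 | -3.88 | -4.06 | -4.04 |
| 1 | -3.42 | -4.14 | -4.03 |

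A separate simulation of 300 runs (true difference -3, patient and night SD both 3.5) let discharge depend on the last night's score at 0.25 log-odds per point. That is 0.25 x sqrt(3.5^2 + 3.5^2) = 1.2 per SD, a strong relation. Completers, about 32 of 50, gave -2.27; the mixed model gave -2.84. The size depends on the assumed mechanism.

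**Planning SD.** The true SD of a 7-night mean is sqrt(16 + 16/7) = 4.28. Completers gave 4.20 (log-odds 0.5) and 3.95 (log-odds 1). The ratios (4.20/4.28)^2 = 0.96 and (3.95/4.28)^2 = 0.85 would make the next trial about 4% or 15% too small. The 95% sampling interval of an SD from 50 patients when the truth is 4.28 is 4.28 x sqrt(chi-square quantile/49), about 3.4 to 5.1. Both completer values lie inside it.

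**The case against.** The protocol never says that incomplete patients will be dropped. That follows only from the classical form of the method; a statistical analysis plan not shown here could fit the same design to unbalanced data. This stands, and it is why the point must be put conditionally.

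The firmly planned analyses are regression and between-group tests. Applied to each patient's mean of observed nights, they keep early leavers at almost no cost. The protocol does not specify that summary, but nothing rules it out. The possible loss is therefore confined to an analysis that is tentative and additional. This also stands, and it lowers the priority.

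Every rate, SD and effect above is assumed, and at 1-2% daily discharge the loss of precision is only 3-6%. That is correct; the range is shown for this reason.

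A reader might go further and infer that the trial's main comparison will be run on completers, or that it will be biased. The documents support neither. They make a link between discharge and sleep possible, through the changing medical situation and the listing of duration of stay as an outcome, but they give no size for it. If discharge is unrelated to sleep there is no bias. Nor do they say that the planning SD will come from completers.

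What the objections do not remove is that the one repeated-measures method named suits the foreseen data less well than an equally accessible alternative.

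**Conclusion.** The point holds as a minor, inexpensive improvement. If classical repeated-measures ANOVA is applied to the 7 nights, about 3 to 20 of 50 patients would be discarded and the standard error would rise by about 3% to 26%, for assumed daily discharge of 1% to 8% and equal patient and night SDs. Bias in the contrast needs a link between discharge and sleep, and is small unless that link is strong. Distortion of the planning SD needs that link and also an SD taken from completers; the values found lie within ordinary sampling variation for 50 patients. As a feasibility study with no power calculation, the trial rests no confirmatory claim on this method.

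**What to change.** In Data analysis, replace repeated-measures ANOVA with a linear mixed model on all observed nights of all randomised patients: arm and night (categorical) as fixed effects, patient as random effect, with music v nature sounds and music v standard care estimated as averages over nights. A simpler and nearly equivalent choice is a t-test or linear regression on each patient's mean of observed nights, built from methods the protocol already names.

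Take the planning SD from all randomised patients, and report discharge before night 7 by arm. Add no baseline sleep covariate, because no baseline sleep score is among the listed entry data: "The patients' baseline characteristics will be noted upon entry into the study: admitting diagnosis, demographics (age, sex) and music sophistication".

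The cost is one or two sentences and slightly more analysis work, with no extra data or patients. The downside is that the mixed model assumes nights are missing at random and, with a single random intercept, that all pairs of nights are equally correlated. Discharge driven by unrecorded health changes would not be covered.
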